The etiology of CPSP has been described as multifactorial, and attributed to the inevitable nerve damage (both directly to nerve and to innervated tissues) and the concomitant release of inflammatory mediators which accompany the surgical procedure. The nociceptive “afferent barrage” associated with the incision and tissue manipulation result in both central sensitization of nociceptive systems and centralization of pain in brain systems^{15,18,25}, theorized to lay the foundation for pain chronification. However, not all patients undergoing surgery will develop CPSP; predictors include factors in cognitive-affective, sociodemographic, genetic, and environmental domains.^{10,15} Most consistently identified as preoperative risk factors for the development of CPSP are, (1) the presence of pain in the body part to be operated on or elsewhere^{9,14,16}, (2) chronic opioid use^{10,11,15,18,26}, and (3) symptoms of psychological distress including depression, anxiety, or pain catastrophizing.^{9,14,16} In fact, predictive evaluations show that the presence of preoperative pain increases the odds of developing 6-month CPSP 2.8 to 4.3 fold, and preoperative distress increases the odds by 3.4.¹⁶ Acknowledging the role preoperative opioid use plays in the development of CPSP, clinical experts are calling for preoperative opioid tapering as an approach to improve post-operative pain outcomes.²⁷

In addition to these preoperative risk factors, the severity of post-operative pain has been identified as an independent predictor of the development of CPSP.⁹ Arguments have been made for each of the identified pre-operative risk factors amplifying post-operative pain severity, in that pre-existing pain brings with it inflammatory and sensitization elements, and antecedent distress results in the patient less able to cope with discomfort. Perhaps most compelling is the role long-term opioid use plays in post-operative pain severity; related to the putative effects of opioid-induced hyperalgesia (OIH),^{28,29} the patient arrives to the surgical setting with opioid-derived increased sensitivity to pain, which becomes evident during the post-operative pain experience. Figure 1 explicates the relationships among these risk factors and the development of CPSP.

Cognitive-Behavioral Therapy for Chronic Pain

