A power analysis was conducted for the post-operative pain outcomes; being a novel intervention, opioid taper outcomes were not considered. Estimated group means, variances, and effect-size were drawn from the literature.^{41,42} The sample size estimate was derived for the primary outcome variable, chronic pain severity, using an expected baseline mean of 4.82 (Effect size: 0.33). Based on estimates obtained, a sample size of 75 participants provides 80% power to detect a pre-post improvement in pain severity (14.5%), depression (21.3%), anxiety (24.3%), and catastrophizing (29.5%), statistically significant at alpha of 0.05. Being a novel intervention, the analysis for chronic post-surgical pain will be considered exploratory and used to obtain effect size estimates. We anticipate a low attrition rate (10%) and will over-recruit 16 additional participants (total 83 subjects per group) to retain adequate power.

2. Key Inclusion Criteria:

[figure not shown]

Figure 1. Predictive factors of CPSP following TKA

1. Males and females, age > 21 years
2. Chronic non-malignant pain of at least 3 months duration
3. Morphine equivalent daily dose (MEDD) > 50 milligrams for at least 3 months
4. Able to enroll at least 4 weeks prior to planned surgery
5. Able to speak, read and comprehend in English at the 6th grade or higher proficiency

Participants will be selected so as to represent the gender, ethnicity, and age of the patient population of individuals seeking TKA in greater Philadelphia area, thus the sample is expected to be 50% women, 55% white, 35% African-American, 6-8% Latino, and 2-4% other or multiracial, and on average 67 years of age. No restrictions on gender or ethnicity will be applied. Because total knee arthroplasty surgery is uncommon in children, individuals under the age of 21 will not be included in this proposed study.

3. Key Exclusion Criteria:

1. Pain of malignant origin
2. Current or past history of opioid use disorder (including those on medication-assisted therapy)
3. Revision of TKA
4. Comorbid CNS disease such as dementia, HIV, psychosis, poorly controlled bipolar disorder or any condition interfering with informed consent

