The research will be conducted in the Department of Orthopaedic Surgery at Penn Presbyterian Medical Center, and data analysis will be performed at the Biostatistics * Evaluation * Collaboration * Consultation * Analysis (BECCA) lab at the U Penn School of Nursing.

The duration of subject participation is approximately seven (7) months beginning four (4) weeks prior to surgery and ending following the 6-month data collection time point. The baseline study session will last approximately 30minutes for those in the control group and 60minutes for those in the experimental group. For those in the experimental group, subjects will spend approximately nine (9) hours prior to surgery receiving the intervention. For those in the control group, subjects will spend approximately four (4) hours prior to surgery receiving the standard educational care. Just prior to the surgery, subjects in both groups spend approximately 45minutes providing pre-operative data, and they will additionally spend one (1) hour providing data at the 3- and 6-month follow up at 30minutes each. Thus, the duration of participation for those in the experimental group is approximately 12 hours, and for those in the control group, approximately 7.5 hours.

METHODS:

1. Study Instruments:

Preoperative chronic pain – The severity of preoperative chronic pain will be evaluated with the Brief Pain Inventory (BPI),⁵² along two dimensions: intensity and interference. Pain intensity is rated on a 0 (no pain) to 10 (worst pain imaginable) scale as the worst in the past 24 hours, least in the past 24 hours, average pain and current pain. Pain interference is measured in 7 areas: general activity, mood, walking ability, work, sleep, enjoyment of life and relationships on a 0 (no interference) to 10 (interferes completely) scale. The composite mean of these scores are used as a pain interference score. BPI scores will be collected prior to the intervention and compared to those collected just prior to surgery and at 3- and 6-month follow-up.

Long-term opioid use – Preoperative opioid use will be measured by converting to morphine equivalent daily dose (MEDD) prior to beginning the intervention, during the study visit just prior to surgery and at the 3 and 6 months follow up if the patients are still taking opioids. At each timepoint, state prescription drug monitoring program will be queried as a check on self-reported opioid use.

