Chronic post-surgical pain – To evaluate for the presence of CPSP, subjects will be asked at 3- and 6-months if they have pain in the surgical site that developed or increased in intensity following the surgery utilizing a checklist based upon the IASP definition of CPSP (Appendix). If they respond affirmatively, BPI pain scores will be collected to assess the intensity and interference associated with the CPSP. In addition, subjects will be asked if they are continuing to use opioids at these timepoints, and if so, daily MEDD calculated for analysis.

2. Group Modifications:

The only group modification with respect to measures is that only those in the intervention group will participate in the survey assessing subject satisfaction with the intervention.

3. Method for Assigning Subjects to Groups:

A randomization scheme will be generated by the study biostatistician and provided to the study coordinator who will assign consecutively enrolled subjects to group.

4. Administration of Surveys and/or Process:

The data collection schedule is described below:

	Baseline (T-4weeks)	Pre-operation (T0)	Post-operation (T = 72hr)	Follow-up (T + 3 and 6 months)
Chronic Pain Intensity (BPI)	X	X		X
Opioid Use (MEDD)	X	X		X
PDMP review	X			X
Pain Catastrophizing (PCS)	X	X		X
Depression & Anxiety symptoms (PROMIS)	X	X		X
CBT use, adherence, satisfaction ^a		X		
Post-operative Pain Severity (72hr VAS)			X	
Post-operative Pain Severity (72hr MEDD)			X	
Chronic post-surgical pain checklist				X

^a subjects in treatment group only

5. Data Management:

Collected data will be entered into the U Penn School of Nursing REDCap (Research Electronic Data Capture) system by trained CITI- and HIPAA-certified research assistants, which is a central and secure resource for data processing and management. As the front-end collection instrument is created, REDCap automatically creates a database designed to store the data that will be recorded from the research. The U Penn School of Nursing has licensed its own version of REDCap that is housed on password protected servers located within a data center inside the School of Nursing firewall, and therefore are afforded the same network protections as other sensitive clinical systems. REDCap was developed specifically around HIPAA-Security guidelines with features such as data encryption and is recommended to Penn researchers by our Office of Human Research.

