Data quality will be monitored by random inspection of the completed datasets by the study coordinator and any problems detected will be discussed with the co-PIs. In addition, the PIs will carefully monitor the data accrual weekly. Data will be entered on an ongoing basis under the direction of the study coordinator, and weekly reports detailing health events, study progress, and data accuracy and completeness will be generated for review by the PIs and co-investigators. Quality assurance activities will be supervised by the study coordinator. Prior to analysis, missing data or discrepancies will be corrected by the project director based on source documents. The study's statistician will analyze the data, using SAS for Windows Version 9.4 statistical software.

Data monitoring of all aspects of this study will proceed in an exacting manner and meet all IRB requirements. Data will be collected by trained research staff using standardized hardcopy and electronic forms and will only be identified with a study ID. Personal identifiers required for follow-up will be linked with the study ID and kept confidential by Drs. [name] and [name] in a secured cabinet. No presentation or publication of the results of this study will refer to the individual participants or present information that would identify any participant. No data will be disclosed to personnel not listed on the study protocol.

6. Subject Follow-up:

Using contact information obtained at the baseline visit, subjects will be contacted via telephone at 3- and 6-months following surgery to determine if CPSP is present utilizing a checklist based upon the IASP definition of CPSP (Appendix). If present, the BPI will be administered, and any opioid use recorded and checked against the PDMP. In addition, the PCS and PROMIS measures will be collected to evaluate the durability of CBT training effects. The sample does not include transient groups, minimizing potential attrition.

STUDY PROCEDURES:

1. Detailed Description:

The study procedures, including all the visits, contacts, and interactions are described sequentially below:

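### The plan does not fix which pain the BPI rates: no body site is stated before surgery, one passage ties the follow-up BPI to surgical-site pain, and the two are compared as change from baseline

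*Combined protocol and SAP*

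**What the plan says.** **Before surgery.** METHODS, 1. Study Instruments (Preoperative chronic pain) uses the BPI for the severity of chronic pain and names no body site. The Key Inclusion Criteria ask for "Chronic non-malignant pain of at least 3 months duration", without limiting it to the knee. The Background lists among the risk factors "the presence of pain in the body part to be operated on or elsewhere".

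**At 3 and 6 months.** METHODS, 1. Study Instruments (Chronic post-surgical pain) asks participants "if they have pain in the surgical site that developed or increased in intensity following the surgery", and for those who say yes it continues: "BPI pain scores will be collected to assess the intensity and interference associated with the CPSP". METHODS, 6. Subject Follow-up and STUDY PROCEDURES, 1. Detailed Description repeat the condition: "If present, the BPI will be administered".

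**Pointing the other way.** The schedule in METHODS, 4 has a single BPI row, labelled as chronic pain intensity and marked at baseline, pre-operation and follow-up, with no footnote. The Appendix checklist starts from a BPI that has already shown persisting pain, and only then asks whether that pain is where the surgery was done.

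**The comparison.** Study Instruments states: "BPI scores will be collected prior to the intervention and compared to those collected just prior to surgery and at 3- and 6-month follow-up". STUDY PROCEDURES, 5. Statistical Analysis summarises the mixed-model results as mean change from baseline by group and time point.

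**The concern.** A change score means something only if the same quantity is rated on both occasions. These patients are on long-term opioids for chronic pain that need not be in the knee. Someone with back and knee pain may rate both before surgery, then be asked at 3 months only about pain arising from the operation. The score can then fall with no change in either pain.

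If the follow-up BPI is general instead, the change score is coherent. The number reported as CPSP intensity then includes pain the operation does not treat, and a between-arm difference in knee pain is diluted.

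The plan's stated goal is reliable effect sizes for larger studies, so either error would be carried into the next design. Site-specific ratings that were never recorded cannot be recovered in the analysis.

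**Working it through.** **1. The plan's own figure.** Target Population and Accrual gives 75 participants, 80% power, effect size 0.33, alpha 0.05 and a 14.5% pre-post improvement from a baseline mean of 4.82. A paired t-test (two-sided) needs n = 74.02, rounded up to 75, and has 80.5% power at 75. The figure reproduces as a within-group pre-post calculation. The target is 0.145 × 4.82 = 0.70 points. It concerns the pre-operative period, where the same unanchored BPI is used at both visits, so this point does not disturb it.

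**2. The two readings side by side.**

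| | Baseline and pre-operation | 3 and 6 months | Consequence |
|---|---|---|---|
| Study Instruments (CPSP paragraph) | site not stated | pain associated with CPSP | change subtracts surgical-site pain from pain of unstated site |
| Schedule and Appendix | site not stated | site not stated | change is coherent, but CPSP intensity is not isolated |

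No passage tells the coordinator which applies.

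**3. Size on the first reading.** The assumptions, none from the documents, are: the unanchored BPI reads the worse of knee and other-site pain; knee mean 4, SD 2; other-site mean 4 or 5, SD 2; the two independent; and a share p of patients with other-site pain. Let D be other-site minus knee pain, with mean m = 0 or 1 and SD 2√2 = 2.83. Moving from overall to knee-only rating lowers the mean by

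fall = p × [m Φ(m/2.83) + 2.83 φ(m/2.83)].

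- For m = 0 the bracket is 2.83 × 0.399 = 1.13.
- For m = 1 it is 0.638 + 2.83 × 0.375 = 1.70.

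Simulation with scores held to 0-10 gives nearly the same values:

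| p | Fall, other-site mean 4 | Fall, other-site mean 5 |
|---|---|---|
| 10% | 0.11 | 0.17 |
| 30% | 0.33 | 0.50 |
| 60% | 0.66 | 1.01 |

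Against 0.70 points this runs from 0.11/0.70 = 0.16 to 1.01/0.70 = 1.44 times the target. With a correlation of 0.5 between the two pains, the 30% to 60% range becomes 0.24 to 0.82 points.

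**4. Size on the second reading.** Under the same assumptions, a 1-point knee shift in one arm is a true difference of 0.96 after the floor at 0. The overall BPI shows:

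| p | Difference seen, other-site mean 4 / 5 | Lost |
|---|---|---|
| 10% | 0.91 / 0.89 | 5.5% / 7% |
| 30% | 0.80 / 0.76 | 17% / 21% |
| 60% | 0.64 / 0.56 | 33% / 41% |

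Losses are computed from unrounded differences.

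**The case against.** The strongest reply is that the schedule and the Appendix describe one general BPI throughout, with the checklist doing the localising. On that reading no change score mixes two pains. This is a fair reading, and it is why the finding is a conflict to reconcile rather than a proven mixture. It does not rescue the CPSP paragraph, which promises an intensity that a general BPI cannot supply.

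Four further points stand:

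- A reader might infer that the pre-operative BPI is defined as pain at any site. The documents do not say so. They leave the site unstated and eligibility unrestricted, and the form's wording is not reproduced.
- A reader might infer that the trial's powered pain outcome is compromised. It is not. Objective 2 compares baseline with pre-operation, objective 3 names 72-hour pain and CPSP rates, and the CPSP analysis is declared exploratory.
- A fall common to both randomised arms largely cancels in a between-arm contrast. It remains in the within-group changes that the plan says it will report.
- The size is driven by assumptions. At 30% prevalence with an other-site mean of 2, the between-arm loss is only 8%. The intervention teaches general coping skills and may reduce other-site pain too, in which case the loss would be smaller.

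Giving the follow-up BPI only to participants with CPSP is a separate problem. Giving it to everyone would still leave open which pain is rated.

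**Conclusion.** The concern holds in a limited form. The reference pain of the BPI is not stated before surgery, one section ties it to surgical-site pain afterwards, and the schedule and Appendix imply otherwise, while the plan compares the scores over time. Followed literally, the CPSP paragraph makes the 3- and 6-month within-group change a difference between two pains. Followed by the schedule and Appendix, CPSP intensity is not isolated.

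Under the worse-of-two-pains model, with 10% to 60% of patients having other-site pain, the spurious within-group fall is about 0.1 to 1.0 points on the first reading, or roughly 5% to 41% of a between-arm knee-pain difference is lost on the second. These are alternatives and should not be added. The documents give no other-site prevalence, so neither range can be narrowed from them.

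The text does not support the claim that the follow-up change certainly mixes two pains, or that every BPI item should have been anchored to the knee. Overall pain is a defensible pre-operative outcome, since the Background counts pain elsewhere as a risk factor. The change is worth making because it is cheap now and impossible after data collection.

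**What to change.** 1. State the BPI reference pain once and use identical wording at baseline, pre-operation, 3 months and 6 months. Keep an overall BPI if overall chronic pain is what objective 2 intends; objective 2 then need not be redefined.
2. At all four time points, add a 0-10 rating of pain in the index knee and one of pain elsewhere.
3. Use the knee rating for CPSP intensity and its change over time. Use the overall BPI for overall pain only.
4. Reconcile both Study Instruments paragraphs, the schedule, Subject Follow-up, Detailed Description and the Appendix on what the follow-up BPI rates and whether it precedes or follows the checklist.

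Cost: an instruction line and one or two short items, with no extra visit and no change to the sample size.

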STUDY DESIGN:

A randomized clinical trial is proposed to evaluate the efficacy of the novel computer-assisted preoperative CBT/opioid sparing intervention to affect acute and chronic post-operative pain outcomes. Specifically, 150 male and female patients meeting study inclusion criteria and preparing to undergo TKA at the Penn Presbyterian Medical Center will be randomized to either receive the computer-assisted preoperative CBT intervention (n=75) or treatment-as-usual (control, n=75). The effectiveness of the intervention to address the preoperative risk factors for CPSP will be evaluated by comparing pain severity, opioid use, symptoms of depression, anxiety and pain catastrophizing before and following the 4-week pre-surgical period and compared within and across subjects. Post-operative pain severity will be abstracted from the electronic health record (EHR) and compared to post-operative pain severity ratings between the intervention and control groups. Similarly, group differences will be inspected for rates of CPSP at 3- and 6-months following surgery. In addition, due to the novelty of the CBT/opioid sparing intervention, brief (15-20min) qualitative interviews will be conducted with the participants who received it during the study visit immediately prior to surgery, to assess patient utilization, and satisfaction with the program in general, and the opioid taper component specifically; adherence is tracked by the PAINTrainer. Participants will be prompted to comment on the perceived ease of use, burden, helpfulness and quality of the CBT intervention.

A randomized clinical trial was designed because it provides the highest level of evidence and lowest risk for bias. The methods employed are predominantly quantitative, although a qualitative survey approach is used to assess subject satisfaction with the intervention. The project is designed, staffed and budgeted to be completed in 24 months. In consultation with consultants, [name] will train the study coordinator coach on delivering the opioid taper intervention during months 1-3, during which time study start-up activities will take place. Enrollment will begin month 3; at a rate of 12-13 enrollments per month, we anticipate having enrolled 166 subjects (n=150, assuming 10% attrition) by study month 15, providing adequate time for 3- and 6-month follow up, and dissemination activities.

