Recruitment and Consent: The EHR of all patients scheduled for TKA at least 5 weeks in the future will be examined to identify those meeting inclusion criteria. Eligibility will be reviewed by Co-I [name]; those eligible will be contacted by the study coordinator to inform them about the study. Those who express interest will be scheduled for a screening visit during which informed consent will be obtained in a Center private room.

Baseline Study Session: Once informed consent is obtained, Baseline measures on the severity of chronic pain, opioid use, pain catastrophizing, and symptoms of depression and anxiety and evidence of OUD will be collected at this time. The PDMP will be consulted to verify self-reported opioid use. In addition, the subjects randomized to the intervention group will be provided access to the computer-assisted preoperative CBT intervention (described below) and trained on its use. It is anticipated this study session will last no longer than 30minutes for those assigned to the control group, and 60 minutes for those assigned to the treatment group.

Pre-operative CBT Intervention: In the current application we will be utilizing and building upon a well-vetted internet-based pain coping skill program (PAINTrainer).⁴¹⁻⁴³ The PAINTrainer includes 8 sessions, each of which takes 35-45 minutes to complete, and teaches an evidence-based pain coping skill. The program is led by a virtual coach and content is provided in audio to minimize reading and facilitate program completion for fatigued or low literacy patients; only key information is highlighted with brief, large-font onscreen text. Illustrations, animations, interactive exercises, and tailored feedback are used to reinforce learning. The intervention can be delivered on a number of platforms (iPad, smart phone, PC, Mac), and four iPads with internet connectivity will be purchased to loan to participants who do not have a device on which to run the application. Users can close a

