Informed consent will be obtained from patients who express interest participating in the study by the trained study coordinator who has experience in obtaining consent from research subjects. It will be obtained in a private office at time that is convenient for the prospective subject. Specifically, the study coordinator will read out loud in English the consent form to the patient, stopping at regular intervals to assess the patient's level of understanding of the information in the consent form, clarifying content, and answering questions. Patients will be told that they need not sign the consent at this time, and that they may take it home to review for as long as they would like prior to deciding to provide informed consent. Patients will be assured that if they choose not to participate, it will have no effect on the medical care they receive or any other social retributions. Any evidence of mental impairment will be evaluated by the study coordinator via informal assessment; if impairment is suspected, the consent process will be halted, and either co-PI [name] or [name] will be called upon to further evaluate.

2. Waiver of Informed Consent:

Not applicable.

RESOURCES NECESSARY FOR HUMAN RESEARCH PROTECTION:

The percent effort and qualifications of the members of the investigative team are more than adequate to conduct the research. Specifically, co-principal investigator, [name] [name] will contribute 1.44 calendar months effort for the duration of the project and take primary responsibility for the development and pilot testing of the cognitive behavioral therapy (CBT) intervention, working closely with consultants [name] and [name]. He will be responsible for training and monitoring the study coordinator/coach to effectively deliver the opioid tapering motivational interviewing (MI) component of the intervention and monitoring the fidelity of this delivery. He will serve as the CBT expert during the efficacy testing of the intervention and troubleshoot any issues that arise as participants undergo the 4-week training. In addition, he will take the lead in directing and interpreting the CBT feasibility and efficacy data in data analysis and dissemination activities and play a primary role in writing reports of the findings and subsequent grant applications.

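### The randomization scheme goes to the coordinator who recruits and consents patients, and no concealment or timed release is described

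*Combined protocol and SAP*

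**What the plan says.** The allocation procedure is one sentence, in item 3 of the Methods section, and it reads: "A randomization scheme will be generated by the study biostatistician and provided to the study coordinator who will assign consecutively enrolled subjects to group". It does not say in what form the scheme is handed over, whether all at once, or at what moment an assignment becomes known.

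The coordinator's other duties are set out elsewhere:

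- **Contact.** In Study Procedures, Recruitment and Consent, the co-investigator reviews eligibility and then "those eligible will be contacted by the study coordinator to inform them about the study".
- **Consent.** In Informed Consent, 1. Consent Process: "Informed consent will be obtained from patients who express interest participating in the study by the trained study coordinator".
- **Enrolment and coaching.** In Resources Necessary for Human Research Protection, the coordinator/coach enrols subjects, schedules their visits, and contacts them weekly before surgery to encourage opioid reduction.

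The only other statement on the mechanism is also in the resources section. It says that randomization will be done through a centralized database of the orthopaedic department.

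The Baseline Study Session covers the baseline measures once consent has been given. In that same session, "the subjects randomized to the intervention group will be provided access to the computer-assisted preoperative CBT intervention".

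Study Design says that a randomized trial was chosen because "it provides the highest level of evidence and lowest risk for bias".

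**The concern.** Randomization protects against selection only if the people who decide whom to approach, consent and enrol cannot tell what the next assignment will be. Here one role receives the scheme and also carries out those steps, and no barrier between the two is described. The same role coaches the intervention arm, so it also has a workload interest in which patients land there. Selection need not involve misconduct. Someone who can see what comes next may approach a keen patient sooner, or schedule a hesitant one later, without meaning to distort anything.

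What is at stake is the plan's own aim. The Statistical Analysis section makes trustworthy effect size estimates for larger studies the primary goal. If the arms differ in who was approached or agreed, the difference enters those estimates. The traits most likely to matter, such as readiness to taper or to work with a coach, are not among the listed baseline measures.

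**Working it through.** The plan gives no figure on this point, so the check sets its sections side by side.

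**Step 1. Who could know the next assignment?** The biostatistician, who generates the scheme, and the coordinator, who is given it (Methods, item 3). If the departmental database is used instead, whoever can view the allocation there could know it. From its place in the resources section, the person said to have full access to that database appears to be the co-investigator who reviews eligibility. The documents do not say whether that access extends to an allocation list.

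**Step 2. What discretion comes before assignment?** The coordinator makes the contact, schedules the screening visit and conducts consent. Under Consent Process, the coordinator also judges mental impairment informally and can halt consent pending evaluation by a co-principal investigator. Patients may take the form home with no time limit, so the date of enrolment is not fixed by the date of contact.

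**Step 3. Is there a barrier between steps 1 and 2?** No section mentions sealed envelopes, central or web release, a third party holding the list, block sizes, or release conditional on consent and baseline. REDCap appears under Data Management for data capture and storage only.

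**Step 4. Do the existing safeguards close the gap?**

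| Safeguard | What it does | What it leaves open |
|---|---|---|
| Records search: "The EHR of all patients scheduled for TKA at least 5 weeks in the future will be examined to identify those meeting inclusion criteria" | Defines a complete candidate pool | Who is contacted, when, and who consents |
| Eligibility review by the co-investigator (Recruitment and Consent) | Limits the coordinator's say over eligibility | Contact, consent and timing; the co-investigator also works with the coordinator on consent (resources section) |
| Consecutive assignment (Methods, item 3) | Fixes the order once patients are enrolled | Who enrols, and in what order |
| Enrolment limit: "Able to enroll at least 4 weeks prior to planned surgery" | Constrains timing | Timing within the limit, and whether a patient is approached |
| Sequential account of procedures (Study Procedures) | Puts consent and baseline measures before program access | When the assignment becomes known; the measures and access share one session |
| Investigator review of accrual; DSMB reports on screening and enrolment | Could reveal a pattern afterwards | Does not stop it from arising |
| Baseline tests and covariates (Statistical Analysis) | Address measured imbalance | Unmeasured differences |

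**Step 5. Do the two statements on mechanism agree?** Item 3 describes a scheme handed to the coordinator and mentions no database. The resources section describes a database and mentions no handover. They could be parts of one procedure, but the text does not join them, and neither describes concealment.

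**The case against.** The strongest reply is that silence is not exposure. Item 3 does not say that the coordinator receives a readable list, or receives it all at once. The departmental database may be the means of concealment, and full access to it need not include the allocation. Item 3 assigns patients who are already enrolled, and the procedures are set out in sequence, with consent and baseline measures ahead of program access. Monitoring is also real: the investigators follow accrual weekly, a co-principal investigator verifies eligibility, and the DSMB sees screening failures and actual against expected enrolment. Finally, the protocol calls this a small pilot study and treats its contrasts as exploratory.

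Much of this stands. A reader might infer that the coordinator holds an open list, or that selective enrolment will occur; the documents support neither. A reader might also combine the enrolment window with the accrual rate to count how many assignments could be foreseen. That count would presuppose an open list, which is the point in doubt, so it is not offered.

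The rest does not answer the point. Assigning after enrolment does not stop the assignment from being known beforehand. Monitoring may detect selection but does not prevent it. Pilot status lowers the stakes for a claim of efficacy, but the plan wants effect sizes to carry forward, and a biased one would carry forward too.

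**Conclusion.** The point holds as a gap in the stated procedure: the recruiter is given the scheme, and nothing described prevents that person from foreseeing assignments. It does not hold as a finding that allocation is unconcealed or that the arms will be unbalanced.

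No size of bias can be derived from the documents, and none is claimed. The conclusion rests on two things: that the coordinator named in the different sections is one role, which the resources section bears out, and that no concealment procedure exists outside these documents. If one does exist, writing it down settles the matter.

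This is a cheap improvement that should be made before the first patient is enrolled. Concealment cannot be restored afterwards. It is not a flaw that makes the trial unsound.

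**What to change.** Reword Methods, item 3 and the database sentence in the resources section so that they describe one route:

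- The biostatistician generates the scheme with randomly varying block sizes and holds it, or loads it into a locked allocation module in the existing REDCap system if one is available. Varying the blocks matters because the coordinator, as coach, knows past assignments and could otherwise work out the end of a block of known size.
- Nobody involved in recruitment, eligibility review or consent can view the scheme. This covers the coordinator and the co-investigator. It also covers the co-principal investigator who verifies eligibility and directs development of the REDCap database, so access rights to any module need to be set accordingly.
- Each assignment is released singly, only after consent is recorded and baseline measures are complete.
- If no module is available, the biostatistician, or another existing team member with no part in recruitment, eligibility or consent, releases assignments one at a time.

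The cost is a small set-up effort and, without a module, someone on call for each release. The resources section lists statistician effort for Year 2 only, while Study Design starts enrolment in month 3, which falls in Year 1. Some of that time must therefore move to before first enrolment. The scheme is needed by then in any case.
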